#### 5.3.3.4. Warnings, Precautions, and Adverse Effects

Common chlorambucil-related toxicities tend to be hematologic: neutropenia, anemia, and thrombocytopenia. Refer to the current chlorambucil package insert for warnings, precautions, and additional adverse effects.

## 6. CONCOMITANT MEDICATIONS/PROCEDURES

Concomitant therapies must be recorded from the time of ICF signing until 30 days after the last dose of study drug.

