#### **5.3.3.2. Dosage and Administration**

Chlorambucil will be administered orally at a dose of 0.5 mg/kg body weight, on Days 1 and 15 of each cycle. On Day 1, chlorambucil will be given as soon as the subject comes into clinic. Pre-medications and obinutuzumab will then be given as outlined in Table 2.

Chlorambucil will be administered in the clinic on days which coincide with concomitant obinutuzumab (Days 1 + 15 of Cycle 1 and Day1 of Cycles 2-6) and will be issued to the subject for home administration on other occasions (Day 15 of Cycles 2-6).

For subjects who have difficulty taking the entire dose of chlorambucil at a single time, the pills may be split up into 2 to 3 batches to be taken over 8 hours on the same day. The dose should not be taken over more than one day.

Unused chlorambucil dispensed during the previous visit must be returned to the site and drug accountability records (Section 12.8) updated at each visit. Returned tablets must not be re-dispensed to anyone.

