### **6.3. Prohibited Concomitant Medications**

Any chemotherapy, anticancer immunotherapy, experimental therapy, or radiotherapy are prohibited while the subject is receiving ibrutinib treatment.

After consultation with the medical monitor the following may be considered; localized hormonal or bone sparing treatment for non-B-cell malignancies, and localized radiotherapy for medical conditions other than the underlying B-cell malignancies.

Erythropoietic growth factors (eg, erythropoietin), platelet growth factors (eg, thrombopoietin) and sargramostim are also prohibited for the first 6 months of study treatment. However, initiation of erythropoietic growth factors (eg, erythropoietin), platelet growth factors (eg, thrombopoietin) and/or sargramostim can be considered after 6 months on study based on the indication outlined in the respective package inserts. Corticosteroids for the treatment of the underlying disease are prohibited. Please refer to Section 6.1 for corticosteroid use in other medical situations.

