##### **7.1.1.4. Prior and Concomitant Medications**

All medications from the signing of ICF through 30 days after the last dose of study drug will be documented. After a subject discontinues study treatment, receipt of all subsequent anticancer therapies will be collected until death, subject withdrawal of full consent, loss to follow-up, or study termination by Sponsor, whichever comes first.

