**7.2.3. Response Categories**

Assessment of response should include physical examination, radiographic imaging, and evaluation of blood and marrow (if applicable). Definition of response for CR, CRi, nPR, PR, and disease progression will be evaluated by the criteria listed in Table 6. Group A criteria define the tumor load and Group B criteria define the function of the hematopoietic system. Response must be confirmed by CT and central labs, and must last at least 2 months without transfusional support or growth factor product to be considered a confirmed response.

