#### 10.7.2.4. Hematological Improvement

Hematological improvement will be evaluated in all subjects and in the subset of subjects with cytopenia(s) at baseline (Hgb  $\leq 11$  g/dL, or platelets  $\leq 100,000/\mu\text{L}$ ), improvement is defined as an increase of Hgb levels from baseline by  $\geq 2$  g/dL, or an increase of platelet counts from baseline by  $\geq 50\%$ . Improvement will be assessed in all subjects at Cycle 9 Day 1 response assessment. Sustained hematologic improvement is defined as hematological improvement that sustained continuously for  $\geq 56$  days without blood transfusion or growth factors.

Percentage of subjects with sustained improvement will be compared using  $\chi^2$  test.

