- u. ECG: At Screening, 12-lead ECGs will be done *in triplicate* ( $\geq 1$  minute apart). ECG's may be performed at the investigator's discretion, particularly in subjects with arrhythmic symptoms (eg, palpitations, lightheadedness) or new onset of dyspnea.
- v. PK (Arm A only): Cycle 1, Day 15: Pre-dose (window: 30-60 minutes before dose), then 1 hour (window: 45-75 minutes), 2 hours (window: 1.5-2.5 hours), and 4 hours (window: 3.5-4.5 hours) post-dose.

- 
- w. PK (Arm A only): Cycle 2, Day 1: To be collected pre-dose only (window: 30-60 minutes before dose).
  - x. Serum chemistry, including creatinine clearance, will only be taken at Cycles 7, 9, 11, 13, 17, 21, 25, 29, 33, and every 6 cycles until PD.
  - y. Protocol visits for subjects on Arm B will occur every 6 cycles until PD beginning at Cycle 39.
  - z. All subjects randomized to study treatment will continue following all study procedures and visits following the pre-PD schedule until disease progression, including subjects on Arm B who complete treatment and any subjects who discontinue study treatment early.

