3.3. Prior and Concomitant Medications

Medications will be coded to preferred term and Anatomical Therapeutic Chemical (ATC) class according to World Health Organization (WHO) Drug dictionary.

Prior medications are defined as medications that started prior to the first dose date of study drug. Concomitant medications are defined as medications that were taken at any time on treatment (i.e. from the date of the first dose of study drug through the date of the last dose of study drug).

Concomitant medications will be summarized by therapeutic class and preferred term in the safety population. The following concomitant medications of special interest will be summarized separately: growth factors, blood supportive products and immunoglobulin, CYP3A inhibitors/inducers, anticoagulants and/or antiplatelet.

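### The protocol's 30-day limit on recording concomitant treatment conflicts with its Pre-PD visit schedule, so equal checking of the no-transfusion, no-growth-factor condition in three secondary endpoints is not assured

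*Protocol*

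**What the plan says.** **Recording rule.** Protocol section 6: "Concomitant therapies must be recorded from the time of ICF signing until 30 days after the last dose of study drug". Section 7.1.1.4: "All medications from the signing of ICF through 30 days after the last dose of study drug will be documented". The only item that section 7.1.1.4 carries past this limit is subsequent anticancer therapy.

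**Treatment length.** Arm B has six 28-day cycles. Section 5.3.3.2: "Chlorambucil will be administered orally at a dose of 0.5 mg/kg body weight, on Days 1 and 15 of each cycle". Section 5.2.1 sets no limit on ibrutinib in Arm A short of progression or unacceptable toxicity.

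**Visit schedule.** Section 8.2 and Appendix A footnote z keep every randomized subject on the Pre-PD schedule until progression (IRC-confirmed, in section 8.2), "including subjects on Arm B who complete treatment and any subjects who discontinue study treatment early". Sections 8.2.1.3 and 8.2.1.4 list both concomitant medications and MRU at the later visits, for both arms. Section 7.1.1.12 defines MRU to include transfusions and hematopoietic growth factors in each arm. Section 10.7.3.5 describes the MRU parameters as numbers of uses.

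**Endpoints that depend on support.** Under section 7.2.3 a response "must last at least 2 months without transfusional support or growth factor product to be considered a confirmed response". Section 10.7.2.4 requires hematologic improvement to hold for at least 56 "days without blood transfusion or growth factors".

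**Growth-factor rule.** Under section 6.3, starting erythropoietic or platelet growth factors or sargramostim "can be considered after 6 months on study based on the indication outlined in the respective package inserts".

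**SAP.** Section 3.3: "Concomitant medications are defined as medications that were taken at any time on treatment", which it spells out as first dose to last dose. It lists growth factors and blood products among the concomitant medications of special interest.

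**The concern.** The recording rule follows study drug, while the endpoints follow the subject to progression. Because Arm B treatment is fixed in length and ibrutinib is open-ended, a rule tied to the last dose gives the arms different lengths of recorded support.

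An absence of support can be verified only over a period in which support is recorded. If a site stops recording at the 30-day limit, an Arm B subject whose counts rose with a transfusion or growth factor after that date looks support-free and is credited. The same event in an Arm A subject still on ibrutinib is recorded and disqualifies.

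The three endpoints are all in the SAP's serial testing order (sections 1.2.2 and 1.6). Among the secondary endpoints, sustained hemoglobin improvement is second, ORR fourth and sustained platelet improvement seventh. A shrunken difference in hemoglobin improvement could close every later test, including MRD-negative response, ORR and OS.

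**Working it through.** The documents give no study day for the end of recording, so there is no stated figure to reproduce. The days below use study day = (cycle − 1) × 28 + day of cycle, for a subject with no dose delays.

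**End of recording in Arm B under sections 6 and 7.1.1.4**
- Last scheduled dose, Cycle 6 Day 15: 5 × 28 + 15 = day 155.
- Recording ends: 155 + 30 = day 185, or 185 / 30.4375 = 6.1 months. This is about when section 6.3 opens the growth factors it had barred.

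**Which 56-day periods fit inside that limit**
- Latest start that fits: 185 − 56 = day 129.
- Cycle 5 Day 1 (first response assessment): 4 × 28 + 1 = day 113; 113 + 56 = day 169. It fits.
- Cycle 7 Day 1: 6 × 28 + 1 = day 169; 169 + 56 = day 225. It does not fit.
- Cycle 9 Day 1: 8 × 28 + 1 = day 225, already 225 − 185 = 40 days past the limit; a 56-day period starting there ends on day 281.

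Under the 30-day rule alone, an Arm B response or improvement present at Cycle 5 can be checked in full. One that starts after about day 129 cannot.

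**What the visit schedule adds**
- Odd-cycle visits from Cycle 9 to Cycle 33: (33 − 9) / 2 + 1 = 13 visits after day 185, identical in both arms, each listing concomitant medications and MRU. Cycle 33 Day 1 is 32 × 28 + 1 = day 897.
- After that, Arm A is seen every 3 cycles from Cycle 36 (day 981) and Arm B every 6 cycles from Cycle 39 (day 1065).

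**Does the schedule override the rule?** The text does not settle it. Adverse events appear on the same late visit lists, yet section 7.1.1.5 and Appendix A footnote i end their collection 30 days after the last dose. A site could read the concomitant-medication item the same way. MRU carries no 30-day limit in section 7.1.1.12, but a continuous 56-day condition needs dates, and the documents describe only counts.

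**What the SAP supplies.** Table 1 and the list after it give no source or window for the support-free condition. The only concomitant-medication window is in section 3.3 and ends at the last dose. In the SAP text available, MRU appears only in the abbreviation list.

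**Size.** The inflation of an Arm B rate would be p × f, where p is the share of Arm B subjects given support after the limit and f is the share of those wrongly credited. The documents give neither.

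**The case against.** The strongest reply is that the protocol already schedules what is needed. All subjects, expressly including Arm B completers, follow the Pre-PD procedures until progression. Both relevant items are on the visit lists, and MRU names transfusions and growth factors in each arm. This stands to a large extent. A reader might infer from section 6 that the condition cannot be checked equally in the two arms; the documents do not support that, because a site following the visit lists would collect the information through the same visits up to Cycle 33.

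Further points stand:
- The case report forms and IRC charter are not available. MRU entries may be dated, and the IRC may receive support data by another route.
- ORR counts best response, so later support does not undo a response already confirmed. Only subjects who qualify solely through a later period are exposed.
- Arm A's limit is not progression itself. A subject who stops ibrutinib for toxicity meets the same 30-day rule.
- It is tempting to count 56 days back from Cycle 9 Day 1 and say that 40 of them are unrecorded in Arm B. Section 10.7.2.4 does not place the 56 days there, so that count is not a property of the endpoint.
- The tables in SAP section 3.3 are descriptive on-treatment summaries, and nothing says the endpoint checks use that definition.
- Any bias runs toward control, so it would not create a false finding of superiority for Arm A.

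The reply does not remove the conflict between the stated rule and the schedule, or the SAP's silence on source and window.

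**Conclusion.** The protocol contradicts itself on how long transfusions and growth factors are recorded as concomitant treatment, and the SAP does not say how the support-free condition is applied. Equal ascertainment in ORR and in sustained hemoglobin and platelet improvement is therefore not assured for Arm B subjects who first qualify after about Cycle 5. It is not shown to be absent.

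The direction, toward the control arm, is conditional: sites must follow sections 6 and 7.1.1.4 rather than the visit lists, and MRU must not supply usable dates. No percentage-point effect can be derived, because the documents give no rates of post-treatment support. Day 185 assumes six cycles completed without delay; early stopping brings the limit forward and delays push it back. The point deserves correction because the condition is built into three gated endpoints and the remedy is small.

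**What to change.** **Protocol sections 6 and 7.1.1.4.** Reconcile both with the Pre-PD schedule. In both arms, record transfusions and growth factors with start and stop dates until the earlier of IRC-confirmed progression or the start of subsequent anticancer therapy, and in any case at least until 30 days after the last dose.

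**SAP.** State that the support-free condition in ORR and in sustained hemoglobin and platelet improvement is applied over this same window in both arms, using the dated concomitant-treatment and MRU records. The on-treatment descriptive tables in section 3.3 may stay as they are.

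**Cost.** Wording in two documents plus case report form guidance, and somewhat more data entry in Arm B. The visits and the concomitant-medication item already exist for that arm. If the MRU form holds no dates, they must be added or taken from the concomitant-treatment form. This is best done early, since undated support may be hard to reconstruct after database lock.

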### 6.1. Permitted Concomitant Medications

Supportive medications in accordance with standard practice (such as for emesis, diarrhea, etc.) are permitted. Use of neutrophil growth factors (filgrastim and pegfilgrastim) or red blood cell growth factors (erythropoietin) is permitted per institutional policy and in accordance with the ASCO guidelines (Smith 2006) except as outlined in Section 6.3 below. Transfusions may be given in accordance with institutional policy.

Corticosteroids at dosages equivalent to prednisone >20 mg/day administered consecutively for >14 days are not allowed.

## 6.2. Medications to be Used with Caution

### 6.2.1. CYP3A Inhibitors/Inducers

Ibrutinib is metabolized primarily by CYP3A4. Avoid co-administration with strong or moderate CYP3A inhibitors and consider alternative agents with less CYP3A inhibition.

- If a strong CYP3A inhibitor (eg, ketoconazole, indinavir, nelfinavir, ritonavir, saquinavir, clarithromycin, telithromycin, itraconazole, nefazadone, cobicistat, or posaconazole) must be used, reduce ibrutinib dose to 140 mg or withhold treatment for the duration of the inhibitor use. Subjects should be monitored for signs of ibrutinib toxicity.
- If a moderate CYP3A inhibitor (eg, voriconazole, erythromycin, amprenavir, aprepitant, atazanavir, ciprofloxacin, crizotinib, darunavir, diltiazem, fluconazole, fosamprenavir, imatinib, verapamil, amiodarone, or dronedarone) must be used, reduce ibrutinib to 140 mg for the duration of the inhibitor use. Avoid grapefruit and Seville oranges during ibrutinib treatment, as these contain moderate inhibitors of CYP3A (see Section 5.3.1.2).
- No dose adjustment is required in combination with mild inhibitors.

Avoid concomitant use of strong CYP3A inducers (eg, carbamazepine, rifampin, phenytoin, and St. John's Wort). Consider alternative agents with less CYP3A induction.

A list of common CYP3A inhibitors and inducers is provided in Appendix C. For further information, please refer to the current version of the ibrutinib IB and examples of inhibitors, inducers, and substrates can be found at <http://medicine.iupui.edu/clinpharm/ddis/main-table/>. This website is continually revised and should be checked frequently for updates.

### 6.2.2. Drugs That May Have Their Plasma Concentrations Altered by Ibrutinib

In vitro studies indicated that ibrutinib is not a substrate of P-glycoprotein (P-gp), but is a mild inhibitor. Ibrutinib is not expected to have systemic drug-drug interactions with P-gp substrates. However, it cannot be excluded that ibrutinib could inhibit intestinal P-gp after a therapeutic dose. There is no clinical data available. Therefore, to avoid a potential interaction in the GI tract, narrow therapeutic range P-gp substrates such as digoxin, should be taken at least 6 hours before or after ibrutinib.

### 6.2.3. Antiplatelet Agents and Anticoagulants

Warfarin or vitamin K antagonists should not be administered concomitantly with ibrutinib. Supplements such as fish oil and vitamin E preparations should be avoided. Use ibrutinib with caution in subjects requiring other anticoagulants or medications that inhibit platelet function. Subjects with congenital bleeding diathesis have not been studied. Ibrutinib should be held at least 3 to 7 days pre- and post-surgery depending upon the type of surgery and the risk of bleeding (see Section 6.4).

Subjects requiring the initiation of therapeutic anticoagulation therapy (eg, atrial fibrillation) consider the risks and benefits of continuing ibrutinib treatment. If therapeutic anticoagulation is clinically indicated, treatment with ibrutinib should be held and not restarted until the subject is clinically stable. Subjects should be observed closely for signs and symptoms of bleeding. No dose reduction is required when study drug is restarted.

### **6.3. Prohibited Concomitant Medications**

Any chemotherapy, anticancer immunotherapy, experimental therapy, or radiotherapy are prohibited while the subject is receiving ibrutinib treatment.

After consultation with the medical monitor the following may be considered; localized hormonal or bone sparing treatment for non-B-cell malignancies, and localized radiotherapy for medical conditions other than the underlying B-cell malignancies.

Erythropoietic growth factors (eg, erythropoietin), platelet growth factors (eg, thrombopoietin) and sargramostim are also prohibited for the first 6 months of study treatment. However, initiation of erythropoietic growth factors (eg, erythropoietin), platelet growth factors (eg, thrombopoietin) and/or sargramostim can be considered after 6 months on study based on the indication outlined in the respective package inserts. Corticosteroids for the treatment of the underlying disease are prohibited. Please refer to Section 6.1 for corticosteroid use in other medical situations.

### **6.4. Guidelines for Ibrutinib Management with Surgeries or Procedures**

Ibrutinib may increase risk of bleeding with invasive procedures or surgery. The following guidance should be applied to the use of ibrutinib in the perioperative period for subjects who require surgical intervention or an invasive procedure while receiving ibrutinib:

#### **6.4.1. Minor Surgical Procedures**

For minor procedures (such as a central line placement, needle biopsy, lumbar puncture [other than shunt reservoir access], thoracentesis, or paracentesis) ibrutinib should be held for at least 3 days prior to the procedure and should not be restarted for at least 3 days after the procedure. For bone marrow biopsies that are performed while the subject is on ibrutinib, it is not necessary to hold ibrutinib.

#### **6.4.2. Major Surgical Procedures**

For any surgery or invasive procedure requiring sutures or staples for closure, ibrutinib should be held at least 7 days prior to the intervention and should be held at least 7 days after the procedure and restarted at the discretion of the investigator when the surgical site is reasonably healed without serosanguineous drainage or the need for drainage tubes.

### **6.4.3. Emergency Procedures**

For emergency procedures, ibrutinib should be held as soon as possible and until the surgical site is reasonably healed or for at least 7 days after the urgent surgical procedure, whichever is longer.

## **7. STUDY EVALUATIONS**

### **7.1. Description of Procedures**

#### **7.1.1. Assessments**

##### **7.1.1.1. ICF**

The subject must read, understand, and sign the Institutional Review Board/Research Ethics Board/Independent Ethics Committee (IRB/REB/IEC) approved informed consent form (ICF) confirming his or her willingness to participate in this study before any study-specific Screening procedures are performed. Subjects must also grant permission to use protected health information per the Health Insurance Portability and Accountability Act (HIPAA) or applicable country regulation. In addition, subjects must sign all approved ICF amendments per the site IRB/REB/IEC guidelines during the course of the study.

##### **7.1.1.2. Confirm Eligibility**

All necessary procedures and evaluations must be performed to document that the subject meets all of the inclusion criteria and none of the exclusion criteria prior to randomization (Section 4).

##### **7.1.1.3. Medical History and Demographics**

The subject's complete history through review of medical records and by interview will be collected and recorded. Concurrent medical signs and symptoms must be documented to establish baseline severities. A disease history, including the date of initial diagnosis will be recorded.

##### **7.1.1.4. Prior and Concomitant Medications**

All medications from the signing of ICF through 30 days after the last dose of study drug will be documented. After a subject discontinues study treatment, receipt of all subsequent anticancer therapies will be collected until death, subject withdrawal of full consent, loss to follow-up, or study termination by Sponsor, whichever comes first.

##### **7.1.1.5. Adverse Events**

The accepted regulatory definition for an adverse event is provided in Section 11.1. All medical occurrences that meet the adverse event definition must be recorded from the time the ICF is signed until 30 days after the last dose of study drug. Laboratory abnormalities designated

clinically significant by the Investigator will also be recorded as adverse events. Additional important requirements for adverse event and serious adverse event reporting are explained in Section 11.4.

#### **7.1.1.6. Physical Examination**

The physical examination will include, at a minimum, the general appearance of the subject, height (Screening only) and weight, and examination of the skin, eyes, ears, nose, throat, lungs, heart, abdomen, extremities, musculoskeletal system, nervous system, and lymphatic system. The lymphatic system examination will include bidimensional measurements of palpable lymph nodes and measurement of spleen and liver sizes by centimeters below the costal margin on the respective side.

*A limited symptom-directed physical examination is required at Cycle 1 Days 8 and 15 visits.*

